8.4.7.2 Concomitant Medications, Supplements, and Other Substances Allowed During the Study

Permitted medications/treatments include any concomitant medication/treatment not listed in the exclusion criteria ([Section 8.3.2](#)).

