8.3.2 Exclusion Criteria

Subjects who meet any of the following criteria will be excluded from the study:

1. Wrinkle Severity Rating Scale Score of ≤ 2 on the right or left nasolabial fold.
2. Women who are pregnant or lactating.
3. Received prior dermabrasion, facelift, or Botox below the orbital rim, or had undergone procedures based on active dermal response (e.g., laser or chemical peeling procedures) within 6 months (180 days) prior to study entry.
4. Use of any facial tissue augmenting therapy with non-permanent filler or aesthetic facial surgical therapy within 9 months prior to study entry.

5. Has ever received semi-permanent fillers anywhere in the face or neck, or is planning to be implanted with these products during the study.
6. Has a permanent implant placed in the NLF area.
7. Evidence of scar-related disease or delayed healing activity within the past 1 year.
8. Scars at the intended treatment sites.
9. History of keloid formation or hypertrophic scars.
10. Any infection or unhealed wound on the face.
11. Allergic history including anaphylaxis, multiple severe allergies, atopy, or allergies to natural rubber latex, lidocaine or any amide-based anesthetic, hyaluronic acid products, or Streptococcal proteins or have plans to undergo desensitization therapy during the term of the study.
12. Aspirin or nonsteroidal anti-inflammatory drugs within 1 week (7 days) prior to treatment.
13. Concomitant anticoagulant therapy, antiplatelet therapy, or history of bleeding disorders, coagulation defects or connective tissue disorders.
14. Over-the-counter (OTC) wrinkle products or prescription wrinkle treatments within 4 weeks (28 days) prior to treatment and throughout the study.
15. Immunocompromised or immunosuppressed.
16. Clinically significant organic disease including clinically significant cardiovascular, hepatic, pulmonary, neurologic, or renal disease or other medical condition, serious intercurrent illness, or extenuating circumstance that, in the opinion of the investigator, preclude participation in the trial.
17. Received any investigational product within 30 days of signing the Informed Consent Form.
18. Facial tattoo that may interfere with diagnosis.
19. Systemic (oral/injectable) corticosteroids or immunosuppressive medications within 30 days prior to treatment and topical steroids on the face within 14 days prior to treatment start and throughout the study.
20. Acne and/or other inflammatory diseases of the skin.

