8.4.3 Administration of Dose for Each Subject

Subjects are physically masked (blindfolded) just prior to and during all injection procedures to prevent observation of the syringes containing study product.

Injections of the study product are performed by the unblinded injecting investigator. The blinded evaluator is not allowed to retrieve study supplies or to be present during opening of the study supplies or during the injections. The injecting investigator is not to have any discussion with the blinded evaluator or subjects regarding the treatments.

Up to a maximum of 2.0 mL (2 pre-filled syringes) will be used per treatment on each nasolabial fold similar to the comparator agent based on previous studies and common clinical practice.

The injection will be given intradermally and for best results should be injected in the mid-dermis. The treatment technique and the volume per treatment should be as similar as possible on both sides of the face.

For many subjects with moderate NLFs, one syringe will be adequate per NLF. Based on the iGAI score at that time, a touch-up treatment may be administered at Visit 2/Week 2.

For this study, topical anesthetic will not be used. Ice may be applied before the treatment if the injecting investigator deems it necessary. The same technique should be used on both sides of the face. Using the nondominant hand to apply gentle downward traction to the inferiormost aspect of the fold to immobilize it, the dominant hand is used to inject filler. Steadying the injecting hand on the mandible or the other hand, the linear threading technique is most easily used to deposit the filler beneath the fold and efface it.

The peri-alar sulcus, a triangular shaped concavity at the upper end of the fold, may be more effectively filled with the fanning technique of implantation, where two or three threads are deposited in a fan-like array. Wide portions of the fold may require several threads placed side by side, with gentle massage after each thread is placed.

Treatment of this area is generally easy and straightforward. Notice that the fold is partially formed by prominent cheek tissue that is lateral to it, with the fold becoming more prominent as the cheek becomes more protuberant. Therefore, injections should stay medial to the fold to fill it. Injecting lateral to the fold, in the excessive cheek tissue, can actually tend to accentuate the fold.

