Bruising is the most common side effect in this area and usually resolves in 5 to 7 days. The facial artery runs below the fold and necrosis is possible, although rare.

Implantation Technique

After removing any make-up, the area to be treated should be cleansed with an alcohol prep pad or some other antiseptic. It is useful to avoid having the subject completely recline as the contours of some facial folds change in the supine position.

The viscosity of stabilized HA gel fillers decreases with increasing temperature. The syringe should be warmed in the hand for a few minutes prior to injection. Use the syringes labeled LEFT to treat the left NLF and the syringe labeled RIGHT to treat the right NLF.

Before injecting the subject, push the plunger forward to feel the intrinsic resistance of the filler moving through the needle, until a small droplet appears at the needle tip. Wipe off the droplet with a sterile pad and begin injection.

The linear threading technique is probably the most commonly used. Holding the syringe parallel to the length of the NLF to be treated, pierce the skin and advance the needle to its fullest extent. Then, while slowly withdrawing the needle, apply even pressure on the plunger to dispense material into dermis. Relieve pressure just before withdrawing the needle from the skin to avoid leakage. Several successive “threads” below, above, or beside previous injections may be required to fill larger folds.

Enter the skin with a needle angle of 30°, 45°, or parallel to the skin. It is recommended to keep the needle bevel up so the tip of the needle is seen and more precisely controlled where the skin is pierced. Keep the tip of the needle at constant depth during implantation, depositing all filler material within the same plane to get even results. The depth of needle placement (and thus filler implantation) should be mid-dermis for NLFs, where the needle’s contour should be visible through the subject’s skin, but the needle’s color is not visible.

After injection, manually massage the area gently to smooth out any nodular or uneven areas, and ensure the implanted material conforms to the contour of surrounding tissues. Using an ice pack or other cold compress can help to minimize swelling and alleviate post injection discomfort.

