8.4.7 Prior and Concomitant Medications/Treatments

All medications and other treatments taken by the subject within 6 months before Visit 1/Day 1 and during the study are to be recorded on the CRF using their generic name, if known, with the corresponding indication. The medications to be recorded include prescription and OTC medications and dietary supplements. All medications taken on a regular basis, including vitamins, aspirin, and acetaminophen, should be recorded prior to first use of the study medication.

The use of any concomitant medication must relate to the subject's documented medical history, prophylaxis, or an AE.

8.4.7.1 Medications, Supplements, and Other Substances Prohibited Before Study Entry and During the Study

The medications prohibited prior to Visit 1/Day 1 are listed in the exclusion criteria ([Section 8.3.2](#)).

Subjects will be advised to avoid the following for the duration of the study:

- Botox® in the study treatment areas
- Any chemical peel (light, medium or deep) in the study treatment areas
- Soft tissue augmentation anywhere on the face
- Dermabrasion or laser abrasion anywhere on the face
- Silicone injections or implants anywhere on the face
- Facial wrinkle therapies, including Accutane® and Renova®
- Aesthetic facial surgery (i.e., facelift)
- Oral corticosteroids or immunosuppressive medications
- Topical corticosteroids on the face
- Treatment with intense pulsed light

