8.8 Efficacy Assessments

8.8.1 Primary Efficacy Endpoint

The primary efficacy endpoint is the proportion of responders immediately after injection, where a responder is defined as a subject who had a within-subject difference (Revanesse Ultra – Revanesse Ultra +) in VAS pain score of at least 10 mm.

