9.6 Sample Size Determination

Restylane-L Injectable Gel was approved in supplement P040024/S039 on January 29, 2010 for mid-to-deep dermal implantation for the correction of moderate to severe facial wrinkles and folds such as NLFs. For the supplement study (MA-1100-001), the primary endpoint was the proportion of subjects who had a within-subject difference in VAS (Restylane minus Restylane-L) pain assessment of at least 10 mm at injection. The objective was to show that the 95% confidence interval for the within-subject difference lay above 50%. The key study results are shown in Table 2 (Source: Summary of Safety and Effectiveness Data (SSED), for Restylane-L Injectable Gel).

Table 2 Subjects with at Least a 10 mm Difference in VAS (Restylane – Restylane-L)

Table 11. Subjects with at least a 10 mm difference in VAS (Restylane - Restylane-L)

Timepoint	No. of subjects with assessments**	Number of subjects with $\Delta \geq 10$ mm			
		n	%	95% LCL	95% UCL
Treatment*	60	43	71.7	58.6	82.5
15 Minutes	60	28	46.7	33.7	60.0
30 Minutes	60	17	28.3	17.5	41.4
45 Minutes	60	10	16.7	8.3	28.5
60 Minutes	60	4	6.7	1.8	16.2

Source: Statistical Report: Appendix 16.1.9, Table 1.23, Appendix 16.2.6.1

*Primary endpoint

**Denominator (N), % = $100 \cdot n/N$

UCL=upper confidence limit; LCL=lower confidence limit

The following sample size is calculated based on the data from the above Restylane-L study, assuming that similar statistics and the same criterion will be applicable for Revanesse Ultra + vs Revanesse Ultra.

Table 3 Sample Size Calculations

Proportion of Responders	Power by N (Number of mITT subjects)	
	N=90	N=80
70%	97.2%	94.1%
68%	93.3%	87.8%

To detect the difference between the null hypothesis proportion of responders of 50% and the alternative proportion of responders of 70% via a two-sided exact binomial test with a 0.05 significance level, 80 mITT subjects will supply a power of 94.1%. For the alternative proportion of responders of 68%, 80 mITT subjects will supply a power of 87.8%.

A total of 100 subjects will be randomized to obtain 80 mITT subjects and to provide adequate data for monitoring safety of the study product.

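### As-needed analgesics and sedatives other than aspirin/NSAIDs are permitted before the Day 1 pain score, which may slightly dilute the 10 mm responder rate; a short pre-injection bar would close the gap cheaply

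*Protocol*

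**What the plan says.** A responder is a subject with a "within-subject difference (Revanesse Ultra – Revanesse Ultra +) in VAS pain score of at least 10 mm" immediately after injection (Protocol 8.8.1). Success requires the exact 95% lower bound for the responder proportion to exceed 50% (Protocol 9.4, SAP 5.5.1).

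Two rules limit other pain relief before that score:
- Protocol 8.3.2, no. 12: "Aspirin or nonsteroidal anti-inflammatory drugs within 1 week (7 days) prior to treatment".
- Protocol 8.4.3: "For this study, topical anesthetic will not be used".

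No other item in 8.3.2 or 8.4.7.1 names acetaminophen, opioids, other analgesics, anxiolytics or sedatives. The default in 8.4.7.2 is permissive: "Permitted medications/treatments include any concomitant medication/treatment not listed in the exclusion criteria". Section 8.4.7 adds one general limit: "The use of any concomitant medication must relate to the subject's documented medical history, prophylaxis, or an AE". It also mentions acetaminophen, but as a drug to record, not one to avoid.

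The mITT definition sets no condition on medication during the visit. PP adds, among other things, the absence of significant protocol violations (SAP section 4), and the medication entry in SAP Table 14.1.4 covers prohibited medications only. Concomitant medications are listed (SAP 5.6.3); no analysis by analgesic use is planned.

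**The concern.** The protocol keeps topical anesthetic away from the pain score but leaves systemic analgesics other than aspirin and NSAIDs, and sedatives, open on the same morning. Taking a permitted drug is not a violation, so a subject who takes one before the Day 1 injections is analysed in both efficacy sets like everyone else.

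The endpoint counts an absolute difference. A drug that reduces pain by the same percentage on both folds also reduces the difference by that percentage, so some subjects who would have reached 10 mm no longer do. At stake are some power against the fixed 50% bar and an understated responder rate. The effect of lidocaine would look smaller than it is without pre-medication.

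**Working it through.** **Inputs from the documents.** Null 50%, alternative 70% (or 68%), two-sided exact binomial test at 0.05, 80 mITT subjects, stated power 94.1% (or 87.8%), 100 randomized (Protocol 9.6). The 10 mm threshold is in Protocol 8.8.1.

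**Inputs assumed.** The documents give no usage rate, drug effect or SD of the within-subject difference D. Assumed: D without the drug is normal with P(D ≥ 10) = 0.70; SD is 15, 20 or 25 mm; 20% of subjects are users; pain on both folds is cut by a fraction c of 0.2 or 0.5.

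**Step 1: the plan's own figure.** The smallest count whose exact 95% lower bound exceeds 50% is 50 of 80 (lower bound 50.96%; 49 of 80 gives 49.70%). P(X ≥ 50 | 80, 0.70) = 94.1%, as stated. At 0.68 the result is 87.90%, against 87.8% stated. For N=100 the critical count is 61 and power at 70% is 97.9%.

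**Step 2: what a proportional cut does.** A user's difference becomes (1 − c)D, so the user responds only if D ≥ 10/(1 − c). That is 12.5 mm for c = 0.2 and 20 mm for c = 0.5.

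**Step 3: user response rate.** The mean is 10 + 0.524 × SD, which is 17.9, 20.5 and 23.1 mm. The user rate is P(D ≥ 10/(1 − c)), and the overall rate is 0.8 × 0.70 + 0.2 × user rate.

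| Pain cut | SD (mm) | User rate | Overall rate | Power, N=80 | Power, N=100 |
|---|---|---|---|---|---|
| none | any | – | 0.700 | 94.1% | 97.9% |
| 20% | 15 | 0.640 | 0.688 | 90.8% | 96.1% |
| 20% | 20 | 0.655 | 0.691 | 91.7% | 96.7% |
| 20% | 25 | 0.664 | 0.693 | 92.3% | 97.0% |
| 50% | 15 | 0.443 | 0.649 | 71.5% | 82.0% |
| 50% | 20 | 0.510 | 0.662 | 79.4% | 88.5% |
| 50% | 25 | 0.549 | 0.670 | 83.5% | 91.5% |

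**Step 4: how much use would matter.** At N=80, power reaches 80% at an overall rate of 0.663. The user share that brings it there is (0.70 − 0.663)/(0.70 − user rate). For a 20% cut this is at least 61%. For halved pain it is 14-25%.

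**Step 5: an equal cut in mm.** If the drug takes the same k mm off both folds, and neither score reaches zero, the difference is (U − k) − (P − k) = U − P, where U and P are the comparator-side and test-side scores. Responder status does not change.

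**Step 6: false-positive risk.** At a true 50% rate the one-sided false-positive probability at N=80 is 1.65%. With 20% users and pain halved it is 0.13% for SD 15 and 0.24% for SD 20, so it falls. More generally, if the two products caused equal pain, randomizing the side makes D symmetric about zero. P(D ≥ 10) then cannot exceed 50%, whatever drug both folds share.

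**The case against.** The strongest reply is that this is a legitimate permissive rule with little room for harm. The population is described as healthy (8.3), significant organic disease is excluded, medications are reviewed at Visit 1 before randomization and injection, and 8.4.7 ties every drug to history, prophylaxis or an AE. The planning rate comes from an earlier filler study (43/60, 71.7%), used while "assuming that similar statistics and the same criterion will be applicable". The protocol does not give that study's medication rules; if they were equally open, part of any loss is already in the 70%. Because the primary score is taken on Day 1, the mITT set may be close to 100, where the loss is smaller. All of this stands, and it is why the point is small. It does not close the gap: prophylaxis can be read to include pre-medication, and no text says otherwise.

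Four stronger readings are tempting, and the documents do not support them:
- **That the trial could succeed falsely.** Each subject is their own control, the side is randomized, and step 6 points the other way.
- **That shared drug use can only lower the rate.** This holds for a proportional cut away from the ends of the scale. An equal mm reduction changes nothing. A sedative that mainly reduced rating noise could raise the rate: with mean 20.5 mm, cutting the SD from 20 to 15 moves P(D ≥ 10) from 0.70 to about 0.76. Pain near the 100 mm ceiling could also reverse the direction.
- **That ice does the same.** Section 8.4.3 says "Ice may be applied before the treatment if the injecting investigator deems it necessary", but goes straight on to require the same technique on both sides. Ice is also local and chosen by the unblinded injector, so it is a different matter from a systemic drug.
- **That pre-injection users could never be identified.** Listing 16.2.9.1 dates drugs by day, while Listings 16.2.5.1 and 16.2.6.1.1 show clock times for injections and scores. However, the medication listing also has an indication column, which would often separate prophylaxis from treatment of an AE. SAP section 6 lets the shells change, and the CRF is not in the documents. Identification is uncertain, not impossible.

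**Conclusion.** The gap is in the text: analgesics other than aspirin/NSAIDs, and sedatives, may be taken as needed before the Day 1 score, and users count fully in mITT and PP. If such a drug reduces pain proportionally on both folds, it can lower the responder rate and cost some power. Validity is not affected.

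The size cannot be derived from the documents. Under the assumed normal model with 20% users, power at N=80 falls from 94.1% to 91-92% for a 20% cut in pain. It reaches 72-84% only if a fifth of subjects take something that halves injection pain. The loss is probably small. This is a cheap improvement, not a defect that puts the conclusion at risk.

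**What to change.** - **Protocol 8.4.7.1:** add that no as-needed or pre-procedure analgesic, sedative or anesthetic other than the study product may be used from 24 hours before the Day 1 injections until the 60-minute VAS, except to treat an AE. If one was taken before injection, Day 1 is postponed. Stable prescribed therapy continues. The 24 hours is a proposal.
- **Protocol 8.4.7.2:** refer to 8.4.7.1 as well as 8.3.2. This is worth doing anyway, because read literally the present text permits treatments that 8.4.7.1 tells subjects to avoid, such as intense pulsed light.
- **Day 1 CRF:** record the clock time of any analgesic or sedative.
- **SAP section 4 and Table 14.1.4:** count barred pre-injection use as use of a prohibited medication, excluded from PP.
- **Optional sensitivity analysis (SAP 5.5.1):** exclude only subjects who took an analgesic or sedative before the immediate VAS. A later dose cannot affect that score and may be taken because of pain, so excluding those subjects would select on the outcome.

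The cost is a short amendment, a time field, a line in the SAP and at most one extra table. A few Day 1 visits would be postponed and PP may be slightly smaller. The mITT definition does not change.

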8.4.8 Assessment of Compliance

Administration of the study product by the investigator is documented on the CRF.

8.5 Study Schedule

The visit-by-visit schedule of study activities is provided in the Study Flow Chart in [Section 3.2](#). The timing of each visit is relative to Day 1, which is defined as the day the subject is randomized and treated.

All visits should be performed within the windows specified on the Study Flow Chart. Every attempt should be made to have each subject attend each visit as scheduled. If a subject is unable to attend a visit within the specified window the visit should be scheduled as closely as possible to the applicable window.

8.6 Study Procedures

The Study Flow Chart in [Section 3.2](#) summarizes the study procedures to be performed at each visit. Individual study procedures are described below.

All clinical assessments (WSRS, pain VAS, and iGAI) must be conducted by qualified investigators listed on the Form FDA 1572 who have been delegated these tasks by the principal investigator (PI). The PI may delegate this task to physicians, physician assistants, or nurse practitioners who have documented training and past experience conducting the assessment.

The WSRS, pain VAS, and iGAI evaluations are to be performed by a research team member who does not participate in treatment and who is blinded to the treatment assignment of each NLF (blinded evaluator).

To minimize variability of evaluations, the same investigator/sub-investigator should perform these assessments for any given subject and anticipate evaluating the subject at each visit, to the extent possible.

8.6.1 Study Initiation

The investigational staff may not enroll any subjects prior to completion of a site initiation visit. This visit will include, but is not limited to, an inventory of study supplies (if present) and a detailed review of the protocol, CRFs, and the investigator's responsibilities as outlined on Form FDA 1572.

8.6.2 Written Informed Consent

The study personnel will review the ICF with each subject and give the subject an opportunity to have all questions answered before proceeding with any study procedures. A copy of the signed ICF will be given to every subject and the original will be maintained with the subject's records.

8.6.3 Significant Medical History/Demographic Information

Medical history and demographic information will be obtained at Visit 1/Day 1. The medical history will include a complete review of all current diseases and their respective durations and treatments. Demographic information will include date of birth, sex, race, ethnicity, and Fitzpatrick skin type (Table 1).

Table 1 Fitzpatrick Classification Scale

Skin Type	Skin Color	Characteristics
I	White; very fair; red or blond hair; blue eyes; freckles	Always burns, never tans
II	White; fair; red or blond hair; blue, hazel, or green eyes	Usually burns, tans with difficulty
III	Cream white; fair with any eye or hair color; very common	Sometimes mild burn, gradually tans
IV	Brown; typical Mediterranean Caucasian skin	Rarely burns, tans with ease
V	Dark Brown; mid-eastern skin types	very rarely burns, tans very easily
VI	Black	Never burns, tans very easily

8.6.4 Physical Examination (Including Vital Signs)

An abbreviated physical examination including height, weight, and vital signs will be recorded. Vital signs will include sitting blood pressure, oral temperature, heart rate, and respiratory rate. This physical examination will be performed at Visit 1/Day 1 to determine that the subject is healthy enough to participate in the study.

